1.7	3/26/20	Changes to I/E criteria, method of patient identification and screening procedures, data collected, and corrected inconsistencies. Additional sites added. Additional blood testing and home blood pressure cuffs added	Y – updated biospecimens and risks
1.8	3/31/20	Clarified I/E criteria, added stopping rules, expanded eligible clinics, clarified table of procedures, clarified reporting of protocol deviations	No

MEDICAL PROTOCOL (HRP-590)

SHORT PROTOCOL TITLE: Randomized control trial of losartan for outpatients with COVID-19

VERSION DATE:5APR2020

ABBREVIATIONS/DEFINITIONS

- COVID-19 Disease caused by the virus SARS-CoV-2, or “Wuhan coronavirus”
- ACE2 Angiotensin converting enzyme 2
- ACE Angiotensin converting enzyme
- ACEi Angiotensin converting enzyme inhibitor
- AE Adverse event
- ALI Acute lung injury
- ARDS Acute Respiratory Distress Syndrome
- ARF Acute respiratory failure
- ARB Angiotensin receptor blocker
- AT1R Angiotensin 1 receptor
- CDR Clinical Data Repository
- CDSS Clinical decision support systems
- CTSI Clinical and Translational Science Institute
- D & I Dissemination and Implementation
- DUA Data Use Agreement
- EBP Evidence-based best practice
- eConsent Electronic consent
- ECMO Extracorporeal membrane oxygenation
- ED Emergency department
- EHR Electronic health record
- FiO2 Fraction of inspired oxygen
- FV Fairview Hospital System
- HCMC Hennepin County Medical Center
- ICD International Classification of Diseases
- ICF Informed Consent Form
- ICS Informatics Consulting Service
- ICU Intensive care unit
- LOS Length of stay
- MHealth University of Minnesota Health
- NETT Neurological Emergencies Treatment Trials
- PaO2 Partial pressure of arterial oxygen
- SAE Severe adverse event
- PETAL Prevention and Early Treatment of Acute Lung injury
- SaO2 Saturation of oxygen
- SIREN Strategies to Innovate Clinical Trials Network
- SOFA Sequential organ failure assessment
- UMMC University of Minnesota Medical Center

Table of Contents

1.0	Objectives	8
2.0	Background	11
3.0	Study Endpoints/Events/Outcomes	15
4.0	Study Intervention(s)/Investigational Agent(s)	17
5.0	Procedures Involved	18
6.0	Data and Specimen Banking	21
7.0	Sharing of Results with Participants	23
8.0	Study Population	24
10.0	Local Number of Participants	32
11.0	Local Recruitment Methods	32
12.0	Withdrawal of Participants	33
13.0	Risks to Participants	34
14.0	Potential Benefits to Participants	35
15.0	Statistical Considerations	35

1.0 Objectives

- 1.1 *Title:* Randomized Controlled Trial of Losartan for outpatients with COVID-19
- 1.2 *Purpose:* To determine the impact of losartan compared to placebo on the rate of hospitalization in outpatients diagnosed with COVID19 not requiring hospital admission at the time of initial presentation.
- 1.3 *Hypothesis:* Losartan will significantly reduce the rate of hospitalization at 15 days in outpatients not requiring hospitalization after initial presentation.
- 1.4 *Study design:* Multi-center, prospective, randomized blinded interventional trial of losartan (25 mg orally twice daily) versus placebo administered for 10 days or until hospital admission.
- 1.5 *Study procedures:*
 - The trial emphasizes early intervention to prevent the progression of respiratory disease. Patients presenting to the emergency department or outpatient drive-thru COVID-19 clinics who test positive for the virus will be eligible for enrollment and randomization within 72 hours of test result and no more than 7 days from symptom onset.
 - Investigators and research coordinators will leverage already functional electronic consent procedures to enroll patients safely while also minimizing risk to study staff. Patients tested at all locations will be given a brochure with study information instructing them to contact the study team if interested in a clinical trial (see attached patient-facing study related materials). In addition, patients receiving test results by phone from the clinical care team will be alerted they may qualify for a research study and that study team members may contact the patient about eligibility. The patient may opt-out of such followup calls. The eConsent platform is currently used in NIH supported StrokeNet and SIREN clinical trials, and are HIPAA compliant.
 - Enrolled patients will be randomized to losartan or placebo, and undergo daily assessment by study personnel with built-in safety and efficacy assessments. Enrolled participants will be delivered study drug, a thermometer, oropharyngeal swabs, home blood pressure cuff, and a urine pregnancy test, if applicable, by courier service within 24 hours of randomization. Study personnel will call patients every other day during the intervention window to review study drug adherence, review symptoms for possible adverse events, remind patients to collect oropharyngeal swabs, and administer validated outpatient dyspnea assessments at predetermined time points.
 - Patient-collected oropharyngeal swabs will be retrieved using a courier service with capacity for transport of biologic specimens to a BSL-3 laboratory (<https://www.researchservices.umn.edu/services-name/biosafety-level-3-program>). These will be stored for public health and viral research purposes.
 - Patients will be followed for 90 days to determine outcomes and the presence of any delayed adverse events. Follow-up phone contact and

electronic medical record review will determine the primary and secondary efficacy endpoints, and provide additional safety data.

1.6 *Data and specimen collection method*

- Inclusion and exclusion criteria, patient demographics, baseline comorbidities, symptoms, and validated symptom assessment measurements by patient self-report, obtained in the medical record, or obtained during an in person pre-screening visit will be collected at the time of enrollment and maintained in a RedCap database. In addition, electronic consent forms will be maintained in a University of Minnesota RedCap database with established functionality currently used by our group for this purpose in our group. The database, with the currently approved eConsent policy, and is HIPAA compliant.
- Every other day follow-ups will be recorded by study personnel into a RedCap database and will include self-reported AEs and medication adherence and maximum daily temperature. On days 0, 4 and 10, a previously validated patient-reported outcomes measurement information system (PROMIS) dyspnea survey and SF-12 (survey's attached in supplement). In the event the patient is not available or contacted on the day of survey administration, surveys administered +/- 1 day will be considered before this data point is considered missing. The following datapoints will also be collected, if available:
 - Name
 - Date of birth
 - Medical record number (if applicable)
 - Phone number
 - Email address
 - Age
 - Gender
 - Race
 - Ethnicity
 - Insurance status (if available)
 - Zip code
 - Location of initial sample collection for diagnosis
 - Location of assessment
 - Date and time of initial sample collection for diagnosis
 - Date and time of positive test result for COVID-19
 - Date of first symptoms
 - Date of first fever (temperature >101.5)
 - Vital signs at presentation (if recorded)
 - Clinical laboratory results at presentation (if recorded)
 - Patient-reported comorbidities [hypertension (requiring or not requiring medication), diabetes mellitus (insulin or non-insulin dependent), coronary artery disease, myocardial infarction, congestive heart failure (with preserved or reduced ejection fraction, if known), pacemaker or AICD, asthma (with or without emergency department evaluation and / or hospital admission in the past year), chronic obstructive pulmonary disease, chronic bronchitis, chronic steroid use, history of transplant (with type),

MEDICAL PROTOCOL (HRP-590)

SHORT PROTOCOL TITLE: Randomized control trial of losartan for outpatients with COVID-19

VERSION DATE:5APR2020

arrhythmias including atrial fibrillation, dialysis, angina, pulmonary hypertension and obstructive sleep apnea, renal disease, liver disease, tobacco and alcohol use history, recent pregnancy or breastfeeding history, height and weight]

- Self-reported home medications [antihypertensives, insulin, non-insulin diabetes medications, corticosteroids (inhaled or systemic), other immunosuppressants hydroxychloroquine, other COVID-directed treatments] or home oxygen use
- Use of outpatient COVID-directed treatments (such as hydroxychloroquine, Tylenol, ibuprofen, azithromycin, or others)
- PROMIS Pool v1.0 Dyspnea Characteristics Survey (5 question Likert scale survey) (attached) with date/time of administration
- Short form 12 (SF-12) health survey (attached) with date/time of administration
- Oropharyngeal swab every third day (performed, yes or no)
- Lowest home blood pressure daily
- Highest home temperature daily
- Medication adherence
- Hospital admission (with date, if applicable)
 - a. If admitted: initial vital signs, initial and highest method of respiratory support (oxygen by nasal cannula, facemask, high flow nasal cannula, CPAP, BIPAP, endotracheal intubation, ECMO), initial and worst measures of organ failure (SOFA score), and initial and worst markers of cardiac injury (troponin, BNP/pro-BNP. CXR or CT chest results will be recorded. If patients are admitted to non-MHealth or HCMC hospitals, we will contact the patient to obtain permission to request data from their hospitalization.
- Date of death (if applicable)
- Study withdrawal, with date and time (if applicable)

- Final outcome follow-ups will be determined through a combination of patient report, electronic medical record review, and review of the social security death index (SSDI).
- All data will be stored in a password protected Redcap database, with customizable tiered access and an audit trail. All protected health information (PHI) will be marked with a PHI tag that will prevent export, so only deidentified data can be exported from the database. Only de-identified data sets with all PHI removed will be shared for the purposes of data analysis.
- Oropharyngeal swabs will be patient-collected and placed in pre-packaged transport to be collected by a biosafety-trained courier service, transported and processed to the University of Minnesota BSL-3 lab, and frozen at -80 C until later analysis. All biospecimens will be labeled with a deidentified patient ID number to prevent inadvertent disclosure of PHI.

The following data points will be collected for biospecimens:

- Study ID number
- Day of protocol

- Specimen tracking number

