4.0 Study Interventions / Interventional Agents

4.1 *Intervention arm:* The intervention is losartan, an angiotensin receptor blocker, in microcrystalline methylcellulose, administered at 25 mg PO twice daily for 10 days (patients with eGFR 30-60 mL/min/1.73 m² will be given 25 mg once daily) or until hospital admission, whichever comes first.

- *Rationale for the duration of the intervention:* The average time from symptom onset to hospitalization based on reports to date is 8-9 days.^{7,31} We expect participants to present with at least 1-2 days of symptoms. We expect most participants to reach their primary endpoint within 10 days of treatment (11-12 days from symptom onset), which represents our time of maximal efficacy of the intervention in this cohort. We have chosen to stop treatment at the time of hospitalization as the participant may or may not be admitted to a participating hospital, introducing significant logistical limitations.
- *Rationale for the dose of treatment:* The lowest dose of losartan is 25 mg orally, which minimize risk of side effects and AEs to the patient. The maximum clinical dose is 100 mg daily. Losartan has a half-life of 2 hours with an active metabolite E3174 of 6-9 hours. The threshold for blockade of angiotensin-II receptor is at least 20 mg per day.³² Twice daily dosing has been shown to potentiate angiotensin-II receptor blockade compared with once daily dosing. We propose a dose of 25mg twice daily. At this dose, extrapolated data suggest 37% inhibition of angiotensin-II receptors, which we believe represents an excellent risk: benefit ratio for trial participants. At the highest maximum allowable clinical dose (50 mg twice daily) we would anticipate 50% inhibition of angiotensin-II receptor.³² Multiple early pharmacokinetic studies of losartan at the low-dose demonstrates the drug has minimal side effects on blood pressure (consistently <10 mmHg reduction in maximal systolic blood pressure) in healthy patients³³⁻³⁶ without an overactive renin-angiotensin-aldosterone system. Clinical exclusion criteria has been added to identify patients who might be at increased risk for side effects. Patients with moderate renal dysfunction (eGFR 30-60 mL/min/1.73 m² will be given 25 mg once daily given impaired renal clearance.

4.2 *Placebo arm.* Placebo capsules will match, and contain microcrystalline methylcellulose only.

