- **Dashboard:** In addition, participating sites have an electronic dashboard or electronic-medical record based report of all pending and confirmed positive COVID-19 tests that can be used for real-time prescreening of emergency department or COVID-clinic patients.

5.2 **Enrollment:** Patients or their legally authorized representative, with due consideration of vulnerable patient populations, (see section 9) will be eligible for consent by delegated members of the study team with appropriate training and experience in the conduct of human subjects research. Enrollment will similarly occur via one of two methods based on location of identification. **In all cases, consent conversations will occur via telemedicine, institutionally approved video connection platform, or phone call (drive through patients or ED patients discharged prior to randomization) which limit traditional face-to-face contact.** If the participant regains capacity to consent, we will reconsent the participant in the study. If they decline, further study procedures will stop but previously collected data under the LAR consent will be utilized. If the participant does not regain capacity to consent, study procedures will continue under consent of the LAR.

- **Rationale for the use of telemedicine, video connection, or phone consent:** We have chosen this method of consent *in order to minimize risk to research team and healthcare providers, and to decrease community spread of the disease.* We have prior experience using telemedicine and phone consent coupled with electronic consent form review for time-sensitive clinical trials of stroke. While the *rationale* for eConsent is different in this case (minimization of disease spread during a pandemic), we believe it is *appropriate* for the disease and intervention being studied. LARs will not be used for remote consent. Critically, the low-dose and established safety profile of losartan, with multiple studies demonstrating minimal side effects on blood pressure in healthy patients³³⁻³⁶ without an overactive renin-angiotensin-aldosterone system, combined with the close remote follow-up methods proposed in this study make the risk: benefit ratio for the alteration of traditional consent process acceptable for participants, providers, and the public.

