5.4 *Patient follow-up:* Participants will receive phone calls by trained study personnel every other day for the 10 days of the intervention period to monitor for the development of complications including lowest daily blood pressure (measured at least once by home blood pressure cuff provided to the patient and medication compliance. Data will be documented into a Redcap database. The coordinators will have participants complete 2 qualitative surveys at enrollment, day 4, and day 10 (both attached in supplement). Surveys and adverse event assessments conducted within 1 day of the time point will be counted as qualifying and not considered missing. At day 15 (+/- 2 day), patients will be asked to return for repeat research blood draw to include creatinine testing. Patients will be contacted by phone at day 28 (+/- 3 days) and 90 (+/- 3 days) for short and intermediate term outcomes. If there is no follow-up due to lack of patient response, this will be documented and not counted as a protocol deviation.

MEDICAL PROTOCOL (HRP-590)

SHORT PROTOCOL TITLE: Randomized control trial of losartan for outpatients with COVID-19

VERSION DATE:5APR2020

5.5 *Table of events:*

		Study Day																			
	Screening / Enrollment ^{t*}	1	2	3	4	5	6	7	8	9	10	11	12	13	14	15	28	90			
ELIGIBILITY																					
Covid-19 Result confirmation	X																				
Inclusion / Exclusion	X																				
Informed Consent	X																				
ADDITIONAL POST-ENROLLMENT PRESCREENING (IF NOT ALREADY AVAILABLE)																					
Pregnancy assessment and birth control X plan**	X																				
Blood Pressure within 1 week of randomization	X																				
Creatinine / Potassium within 1 week of randomization	X																				
Randomize subject if eligible after additional prescreening	X																				
POST-RANDOMIZATION																					
Demographics	X																				
Medical History / CRF	X																				
Dispense / administer study drug**	X	X	X	X	X	X	X	X	X	X	X										
STUDY PROCEDURES (while outpatient) #																					
Assessment of Hospitalization			X		X		X		X		X								X	X	
Adverse event assessment			X		X		X		X		X								X	X	
Review adherence			X		X		X		X		X										
Review and record blood pressures and temperatures			X		X		X		X		X										
PROMIS Survey					X							X							X		

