10.0 Local Number of participants

10.1 *Locations:* Enrollment will occur in the ED (or designated COVID19 areas) of MHealth Fairview Southdale Hospital, MHealth Ridges Hospital, University of Minnesota Medical Center East Bank and West Bank, Hennepin County Medical Center, Bethesda Hospital (COVID designated hospital, Mayo Clinic St. Mary's Hospital, or remotely via

the previously described methods for interested participants presenting to one of the 4 drive-thru clinics or stand-alone COVID clinic.

10.2 Number of participants: We will enroll 580 participants; this will provide adequate statistical power for testing our primary hypothesis and allows for 10% loss-to-follow-up.

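### Inpatient data from hospitals outside MHealth and HCMC depend on the patient's permission after admission, with no stated proxy, leaving secondary severity outcomes open to severity-related loss

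*Combined protocol and SAP*

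**What the plan says.** Section 1.6, in the item on data collected after a hospital admission, lists initial vital signs, initial and highest respiratory support, initial and worst SOFA, cardiac markers and chest imaging. It then says: "If patients are admitted to non-MHealth or HCMC hospitals, we will contact the patient to obtain permission to request data from their hospitalization". The evident meaning is hospitals outside both systems.

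Section 4.1 expects such admissions. It explains stopping treatment at hospitalization partly by noting that "the participant may or may not be admitted to a participating hospital".

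Section 10.1 names "Mayo Clinic St. Mary's Hospital" among the enrolling locations, but the 1.6 sentence exempts only MHealth and HCMC.

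On other sources, 1.6 says: "Final outcome follow-ups will be determined through a combination of patient report, electronic medical record review, and review of the social security death index". Section 5.4 sets calls every other day during the 10-day intervention, a requested return visit at day 15, and calls at days 28 and 90. On failed contact it says: "If there is no follow-up due to lack of patient response, this will be documented and not counted as a protocol deviation".

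On proxies, 5.2 says: "LARs will not be used for remote consent". That rule is written for enrollment consent. No passage names a proxy for releasing outside hospital records. The data list in 1.6 holds the participant's own phone and email and no second contact.

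Section 16.9 has participants sign an authorization to use and disclose health information before enrollment. It does not say whether this covers release by an outside hospital.

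**The concern.** The people whose inpatient data matter most for severity are the least able to answer a request for permission. Section 21.8 itself describes patients without capacity as often intubated, delirious or sedated. A participant on a ventilator in an outside ICU cannot agree at that time, and one who dies there never can. A participant with a short, mild outside stay can agree by phone.

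The outcomes at stake in 3.2 are ventilator- and oxygen-free days, the 7-point scale at days 7, 15 and 28, and admission with oxygen therapy at day 15. The respiratory support and SOFA measures in 1.6 are exposed too. If an outside admission is known but its chart is not available, the participant can be placed somewhere in ordinal levels 2-5 while hospitalized, but not at a particular level. Section 15 allows for 10% loss to follow-up and gives no rule for missing severity outcomes, so nothing in the analysis plan addresses loss of this kind.

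**Working it through.** **Inputs**
- Admission rates 15% (control) and 7% (losartan); 264 evaluable and 290 enrolled per arm: section 15.2.
- ICU share of hospitalized patients, 13 of 50: the New York count in section 3.3. It is used only as a rough guide.
- Share *s* of admissions outside the named hospitals: not given. Assumed range 10-30%.

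**1. The plan's own figure.** With d = 0.08 and mean rate 0.11, the uncorrected two-proportion formula gives

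n = [1.960 × √(2 × 0.11 × 0.89) + 0.842 × √(0.15 × 0.85 + 0.07 × 0.93)]² / 0.08² ≈ 239 per arm.

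The continuity correction, (n/4) × [1 + √(1 + 4/(n × d))]², gives 264, which matches 15.2. Then 264 × 1.10 = 290.4, against the 290 enrolled. The rates and sample size are therefore a sound base for counting admissions.

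**2. Expected admissions.**
- 290 per arm: 290 × 0.15 + 290 × 0.07 = 43.5 + 20.3 = 63.8.
- 264 per arm: 39.6 + 18.5 = 58.1.

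**3. Expected ICU-level cases.** 13/50 = 26%.
- 63.8 × 0.26 = 16.6.
- 58.1 × 0.26 = 15.1.

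**4. Cases that depend on later permission** (counts × *s*):

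| *s* (assumed) | Outside admissions, 290 per arm | ICU-level among them | Outside admissions, 264 per arm | ICU-level among them |
|---|---|---|---|---|
| 10% | 6.4 | 1.7 | 5.8 | 1.5 |
| 20% | 12.8 | 3.3 | 11.6 | 3.0 |
| 30% | 19.1 | 5.0 | 17.4 | 4.5 |

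The ICU columns are ceilings. They count a case as lost only if permission is never obtained, and they suppose that this happens for every outside ICU-level case.

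**5. What the ceiling would do to a severity comparison.** Apply 26% in both arms at 290 per arm: 43.5 × 0.26 = 11.3 and 20.3 × 0.26 = 5.3 ICU-level cases, a difference of 6.0. Losing 30% in each arm leaves 7.9 and 3.7, a difference of 4.2. Equal fractional loss shrinks the absolute difference and leaves the ratio unchanged.

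**6. Which outcomes depend on the permission.** The 1.6 sentence applies to a participant already known to be admitted, because the team cannot ask about a stay it has not heard of. Admission is found through the calls, the day-15 visit, patient report and record review. Section 18.3 also treats hospitalization as a serious adverse event reported within 24 hours. Death has the death index. What remains behind the permission is the content of the inpatient chart: respiratory support, SOFA, oxygen and ventilator days, and the choice among ordinal levels 2-5.

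**The case against.** The strongest reply is that the loss may be small or already prevented.

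- **The authorization.** The document in 16.9 may include an outside-hospital release, and the consent forms may ask for a second contact. Neither can be seen here. This stands, and it is why confirming the existing wording is an acceptable form of the fix. It does not remove the point, because 1.6 as written still sends the team to the patient.
- **No deadline.** Section 1.6 sets no time limit, follow-up runs to day 90, and 12.3 locks the data within a year of the last enrollment. A survivor who recovers can agree, and the chart then supplies everything retrospectively. This stands. Permanent loss is confined to those who die, stay incapacitated, refuse or cannot be reached.
- **Small numbers.** Five cases are under 1% of 580 (5/580 = 0.9%). That is true of the whole trial, but the severe end rests on about 17 cases.
- **The Mayo wording.** It may be a lag after sites were added. Even so, the sentence needs editing.

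A reader might go further and infer that the primary endpoint is lost for outside admissions, or rests on patient report alone. The documents do not support that. The permission step presupposes a known admission, and several sources are named. An outside stay could still be missed if the participant cannot be reached and the local record does not show it. That comes from reliance on contact, not from the 1.6 sentence.

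A reader might also take 5.4 as ending ascertainment after a missed call. It only says that non-response is documented and is not a deviation.

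Nor is the bias always toward no difference. That direction follows for the absolute difference in identified severe cases when capture fails equally in both arms; unequal capture could move the comparison either way.

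**Conclusion.** The point holds for secondary severity outcomes. Following 1.6 as written exposes inpatient data from outside hospitals, and read literally from one enrolling hospital, to loss that is plausibly related to severity. No proxy route is stated.

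About 6-19 of 64 expected admissions would depend on later permission (about 6-17 of 58 with 264 evaluable per arm), and at most about 2-5 ICU-level cases could be lost. These figures rest on the plan's rates, the early New York ICU share and an assumed 10-30% outside share. The upper end also supposes that no outside ICU-level patient's permission is ever obtained. That sicker patients lose more data is an inference from the mechanism; no figure in the documents measures it.

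No effect on the primary endpoint or its power follows from this rule. The change is worth making because it is cheap at enrollment and cannot be fully repaired for participants who die or stay incapacitated.

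**What to change.** 1. **At enrollment, in the eConsent:** obtain a release covering records from any hospital, ED or clinic through day 90, or confirm that the 16.9 authorization already does this and say so in the protocol. Collect one alternate contact.
2. **Section 1.6:** replace the quoted sentence with 'records will be requested under the release signed at enrollment', and state that it covers every hospital, including Mayo Clinic St. Mary's.
3. **Section 5.4:** add that an unanswered scheduled call leads to contact with the alternate person.

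The cost is one release and one contact field in an existing eConsent, IRB approval of the wording, and a slightly longer consent conversation. If the current authorization already suffices, the record-release part reduces to editing the text. The change reduces the amount of missing severity data; it does not replace a missing-data rule in section 15, which is a separate matter.
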